5.6.1. Patients with the Procedure

The procedure that patients are applied will be summarized for the Safety population by treatment group and overall.

The study duration will be calculated as the number of days between the randomization and study exit, inclusively (study exit day – randomization date + 1). The study duration will be summarized using descriptive statistics by treatment group and overall.

5.6.1.1. Treatment Compliance

Not applicable

CONFIDENTIAL

Draft Statistical Analysis Plan v2.0

XEN-45 Gel Stent

5.6.2. Adverse Events

Adverse events will be coded by system organ class (SOC) and preferred term (PT) using the Medical Dictionary for Regulatory Activities (MedDRA), version #21.0 or newer.

Adverse events will be classified to either ocular AEs or nonocular AEs. An ocular AE will be determined as indicated on the AE form of eCRF, and thus are not limited to AEs with primary SOC of eyes. The adverse events will be also classified to either AE or adverse device effect (ADE). The summary of AEs will be separately done for nonocular AEs, ocular AEs and ADEs. Ocular AEs and ADEs will be tabulated by treatment group for the study, and nonocular AEs will be summarized by treatment group for participants. eye

An AE will be considered a treatment emergent adverse event (TEAE) if the AE began or worsened (increased in severity or became serious) on or after the date (and time, if known) of the surgery.

An TEAE and ADE will be considered a TESA or SADE if it meets any SAE criterion.

Overall summary of TEAEs will be provided for categories of all TEAEs, treatment-related TEAEs/TEADEs, TESA/TEADE, deaths, TEAEs/TEADEs leading to study discontinuation, TEAEs/TEADEs, treatment-related TEAEs/TEADEs, TESA/TEADEs and TEAEs/TEADEs leading to study discontinuation will be further classified into ocular and nonocular subcategories.

The number and percentage of participants reporting TEAEs/TEADEs in each treatment group will be tabulated by SOC in descending frequency order of XEN first, then by preferred term in descending frequency order of XEN, and further categorized by severity. If more than 1 AE/ADE is coded to the same preferred term for the same participant, the participant will be counted only once for that preferred term using the greatest severity and strictest causality for the summarization by severity and causal relationship.

The number and percentage of participants with treatment-related TEAEs/TEADEs will be tabulated by SOC and preferred term.

Summary tables will be provided for participants with TESA and participants with TEAEs/TEADEs leading to discontinuation. Listings of all AEs, SAEs, and AEs leading to discontinuation by participant will be presented.

The same analysis will be repeated for ocular TEAEs/TEADEs, ocular TESA/TEADEs.

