#### **8.4.1.2 Comparator – Trabeculectomy**

Trabeculectomy will be performed in accordance with the standard of care at each investigative center with adjunctive antifibrotic therapy and including essential steps: conjunctival flap, scleral flap, and sclerostomy. Note: Peripheral iridectomy is not mandated and is left to the standard practice of the surgeon.

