### **10.1.2 Safety Analysis**

Safety analysis will be performed in both the XEN population and the population randomized to trabeculectomy. The numbers and percentage of subjects reporting AEs will be tabulated regardless of causality. AEs, ADEs, and all safety measures will be summarized by frequencies at each visit.

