#### **Adverse Device Effect (ADE)**

An ADE is defined in accordance with ISO 14155 as “an adverse event related to the use of an investigational medical device.” This definition includes any AEs resulting from insufficient or inadequate instructions for use, deployment, implantation, installation, or operation, or any malfunction of the investigational medical device as well as any event resulting from use error (per ISO 62366) or from intentional misuse of the investigational medical device.

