5.6.2.1. Adverse Events of Special Interest

Intraoperative AEs

- Detached Descemet's membrane
- Iris damage
- Lens contact
- Vitreous bulge or loss
- Anterior chamber bleeding

CONFIDENTIAL

Draft Statistical Analysis Plan v2.0

XEN-45 Gel Stent

- Retrobulbar hemorrhage
- Conjunctival perforation
- Conjunctival or scleral flap tearing
- Shallow anterior chamber with peripheral iridocorneal touch
- Flat anterior chamber with iridocorneal touch extending to the pupil
- Device malfunction identified prior to implantation
- Choroidal hemorrhage or effusion

Postoperative AEs

The following is a list of AEs that can occur postoperatively for XEN and/or trabeculectomy surgery.

- Angle recession
- Anterior chamber shallow with peripheral iridocorneal touch
- Anterior chamber flat with iridocorneal touch
- BCVA loss of ≥ 2 lines (≥ 10 Early Treatment Diabetic Retinopathy Study [ETDRS] letters)
- ≤ 30 days
- > 30 days
- At 12 months (persistent loss)
- Bleb leak (without operative room or slit lamp revision)
- Bleb leak (with operative room or slit lamp revision)
- Blebitis (with or without anterior chamber reaction or hypopyon)
- Cataract formation
- Clinically significant progression of cataract, based on an assessment by the investigator
- Choroidal effusion (extending posterior to equator, without blood)
- Choroidal effusion (obscuring disc or macula, without blood)
- Choroidal effusion (with choroids touching in the center of the eye, without blood)
- Choroidal effusion (extending posterior to equator, with blood)
- Choroidal effusion (obscuring disc or macula, with blood)
- Choroidal effusion (with choroids touching in the center of the eye, with blood)
- Choroidal effusion and/or hemorrhage occurring > 30 days (persistent)
- Chronic pain (present greater than 3 months)
- Corneal edema grade 3 or grade 4 (> 30 days postoperatively)
- Cyclodialysis
- Dellen
- Device malfunction
- Endophthalmitis
- Fixed dilated pupil
- Hyphema (≥ 2 mm in height [layered] at any time)
- Hyphema (present or arising > 30 days)
- Hypotony (IOP < 6 mm Hg at any time)

CONFIDENTIAL

Draft Statistical Analysis Plan v2.0

XEN-45 Gel Stent

- Persistent hypotony (IOP <6 mm Hg at 2 visits >30 days apart)
- Hypotony maculopathy
- Implant exposure
- Implant fracture
- Implant migration
- Implant obstruction (complete or partial)
- Implant repositioning requiring surgical intervention
- Increase in cup/disc ratio of ≥ 0.3 units on slit lamp examination

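### SAP 5.6.2 is inconsistent on whether device-related events count in the ocular AE tables; read literally, its AE-or-ADE sort would take them out of the XEN arm only

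*SAP*

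**What the plan says.** SAP 5.6.2 (Adverse Events) first divides events into ocular and nonocular. Using the same either/or construction, it then adds a second division: "The adverse events will be also classified to either AE or adverse device effect (ADE"). Two sentences make this operational: "The summary of AEs will be separately done for nonocular AEs, ocular AEs and ADEs", and "Ocular AEs and ADEs will be tabulated by treatment group for the study".

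Later in the section the labels change. "Overall summary of TEAEs will be provided for categories of all TEAEs, treatment-related TEAEs/TEADEs", and further categories follow. The system organ class and preferred term table, and its ocular repeat, carry the joint label TEAEs/TEADEs. The SAP does not say whether that label means one combined table or two parallel ones.

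The protocol (Adverse Device Effect definition) describes an ADE as "an adverse event related to the use of an investigational medical device". Protocol 10.1.2 adds: "The numbers and percentage of subjects reporting AEs will be tabulated regardless of causality".

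**The concern.** Under the protocol, every ADE is an AE. A rule that puts each event in one class or the other, and then summarises the classes apart, makes entry to the AE table depend on whether the investigator judged the event device-related. Protocol 10.1.2 rules that out.

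If the rule were followed, its effect would fall on one arm. An ADE needs an investigational device, and trabeculectomy as described in Protocol 8.4.1.2 uses none. A choroidal effusion judged device-related in a XEN eye would go to the ADE table. The same effusion after trabeculectomy could only go to the ocular AE table. The ocular AE table would then understate XEN, and the ADE table would set XEN against a column that is empty by construction. The causality judgement that decides the table is made by an investigator in an open-label trial. Comparing safety between the arms is part of the stated objective, so the construction of these tables matters even though no safety hypothesis is tested.

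**Working it through.** The plan gives no figure on this point to reproduce. The check is a comparison of texts, followed by an illustration of size.

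**1. Text that points to separate counting (SAP 5.6.2)**
- The AE/ADE sentence repeats the form of the ocular/nonocular split, which is mutually exclusive.
- Nonocular AEs, ocular AEs and ADEs are to be summarised separately.
- The seriousness rule treats TEAE and ADE as parallel classes, each with its own serious counterpart.

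**2. Text that points to combined counting (SAP 5.6.2 and 5.6.2.1)**
- A TEAE is defined by onset or worsening on or after surgery. A device-related event meets that definition, and none is carved out.
- The overall summary has a category for all TEAEs.
- A participant with more than one AE/ADE under the same preferred term is counted once, at the strictest causality. That rule is most natural if both kinds of event share a table.
- Section 5.6.2.1 lists implant exposure, fracture and migration, and explant, as AEs of special interest.

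The two sets do not agree. SAP section 1 places the table specifications in a separate document that is not among those reviewed, so they cannot decide it.

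**3. Is the effect one-sided?**
- The comparator is a surgical procedure: "Trabeculectomy will be performed in accordance with the standard of care at each investigative center with adjunctive antifibrotic therapy". The essential steps listed with it include no investigational device.
- SAP section 4 analyses the Safety population by actual surgery. An eye assigned to trabeculectomy that received XEN would therefore count under XEN.
- One event list serves both procedures: "The following is a list of AEs that can occur postoperatively for XEN and/or trabeculectomy surgery". It includes hypotony and choroidal effusion.

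ADEs can therefore arise essentially only in the XEN column, while the clinical events themselves can occur in both.

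**4. Size under the exclusive reading**

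Let r be the true proportion of eyes with an ocular AE, equal in both arms. Let s be the share of affected XEN eyes whose only ocular events were classed as ADEs. Both are assumptions; neither document gives them.

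- XEN rate shown in the ocular AE table = r × (1 − s)
- Trabeculectomy rate shown = r
- Apparent difference, XEN minus trabeculectomy = −r × s

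| r | s | XEN shown | Trabeculectomy shown | Apparent difference |
|---|---|---|---|---|
| 10% | 25% | 7.5% | 10% | −2.5 points |
| 10% | 75% | 2.5% | 10% | −7.5 points |
| 20% | 25% | 15% | 20% | −5 points |
| 20% | 50% | 10% | 20% | −10 points |
| 20% | 75% | 5% | 20% | −15 points |
| 30% | 25% | 22.5% | 30% | −7.5 points |
| 30% | 75% | 7.5% | 30% | −22.5 points |

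In eyes, using the SAP section 3 enrolment minimum of 76 XEN and 38 trabeculectomy: at r = 30% the true expected counts are 0.30 × 76 = 22.8 and 0.30 × 38 = 11.4. With s = 75%, the XEN ocular AE table would show 22.8 × 0.25 = 5.7 of 76.

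**5. Size under the inclusive reading**

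ADEs stay in the ocular AE table, so s = 0 and the apparent difference is 0.

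**The case against.** The strongest reply is that this is loose drafting and the protocol resolves it. The SAP presents itself as an elaboration of the protocol, and its Appendix 2 lists only the sample-size reduction as a change to planned analyses. On that view, separate summaries of ADEs merely show a subset in an extra table. The ocular tables, labelled TEAEs/TEADEs, already contain device events. The all-TEAEs category, the TEAE definition and the once-only count support this.

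Much of that stands. A reader might infer that XEN device-related events are certain to be missing from the ocular AE table, or that they drop out of the report. The documents support neither. Removal is one of two readings, and even under it ADEs are tabulated by treatment group and all AEs are listed by participant. Clinical hypotony, and eyes with IOP of 6 mm Hg or less, are also separate safety endpoints that do not depend on an AE/ADE label. It is fair, too, that the rates and shares in the illustration are assumed.

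What does not stand is that the protocol settles the matter in practice. The either/or sentence and the separate-summary sentence are explicit instructions, and a programmer could reasonably build disjoint tables from them. The slash in TEAEs/TEADEs is never explained. If ADEs were already within TEAEs, the second label would be unnecessary.

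**Conclusion.** The point holds as an inconsistency with a conditional consequence. The either/or sentence in SAP 5.6.2 contradicts the protocol's definition of an ADE and its rule of tabulating AEs regardless of cause, and it also disagrees with other text in its own section. Whether the ocular AE comparison would actually be distorted cannot be determined from the protocol and SAP.

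The size runs from zero (ADEs included) to between 2.5 and 22.5 percentage points in favour of XEN (ADEs excluded). The upper range rests on equal true ocular AE rates of 10% to 30% and on 25% to 75% of affected XEN eyes having only device-related ocular events. It should not be quoted as an expected bias. No safety hypothesis test is affected. The change is worth making because the possible error runs in one direction, bears on a comparison named in the objective, and is cheap to rule out.

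**What to change.** In SAP 5.6.2:

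1. Replace the either/or sentence with a statement that every ADE is also an AE, with ADE and SADE carried as flags on the event.
2. State that all between-arm tables of ocular TEAEs and serious TEAEs in the study eye include ADEs, regardless of causality. Define TEAEs/TEADEs to match, or drop the second label.
3. Base the between-arm treatment-related table on relatedness to the device or to the study procedure. The protocol's causality section already has investigators assess both. The SAP does not define treatment-related for trabeculectomy, so this closes that gap too.
4. Present ADE/SADE as an additional table, with a note that it is not a between-arm comparison.

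Carry the same wording into the table shells. The cost is edits to the SAP and shells, with no new data collection. The downside for the sponsor is that XEN AE percentages may be less favourable than under a literal split.

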5.6.2.1. Adverse Events of Special Interest

Intraoperative AEs

- Detached Descemet's membrane
- Iris damage
- Lens contact
- Vitreous bulge or loss
- Anterior chamber bleeding

CONFIDENTIAL

Draft Statistical Analysis Plan v2.0

XEN-45 Gel Stent

- Retrobulbar hemorrhage
- Conjunctival perforation
- Conjunctival or scleral flap tearing
- Shallow anterior chamber with peripheral iridocorneal touch
- Flat anterior chamber with iridocorneal touch extending to the pupil
- Device malfunction identified prior to implantation
- Choroidal hemorrhage or effusion

Postoperative AEs

The following is a list of AEs that can occur postoperatively for XEN and/or trabeculectomy surgery.

- Angle recession
- Anterior chamber shallow with peripheral iridocorneal touch
- Anterior chamber flat with iridocorneal touch
- BCVA loss of ≥ 2 lines (≥ 10 Early Treatment Diabetic Retinopathy Study [ETDRS] letters)
- ≤ 30 days
- > 30 days
- At 12 months (persistent loss)
- Bleb leak (without operative room or slit lamp revision)
- Bleb leak (with operative room or slit lamp revision)
- Blebitis (with or without anterior chamber reaction or hypopyon)
- Cataract formation
- Clinically significant progression of cataract, based on an assessment by the investigator
- Choroidal effusion (extending posterior to equator, without blood)
- Choroidal effusion (obscuring disc or macula, without blood)
- Choroidal effusion (with choroids touching in the center of the eye, without blood)
- Choroidal effusion (extending posterior to equator, with blood)
- Choroidal effusion (obscuring disc or macula, with blood)
- Choroidal effusion (with choroids touching in the center of the eye, with blood)
- Choroidal effusion and/or hemorrhage occurring > 30 days (persistent)
- Chronic pain (present greater than 3 months)
- Corneal edema grade 3 or grade 4 (> 30 days postoperatively)
- Cyclodialysis
- Dellen
- Device malfunction
- Endophthalmitis
- Fixed dilated pupil
- Hyphema (≥ 2 mm in height [layered] at any time)
- Hyphema (present or arising > 30 days)
- Hypotony (IOP < 6 mm Hg at any time)

CONFIDENTIAL

Draft Statistical Analysis Plan v2.0

XEN-45 Gel Stent

- Persistent hypotony (IOP <6 mm Hg at 2 visits >30 days apart)
- Hypotony maculopathy
- Implant exposure
- Implant fracture
- Implant migration
- Implant obstruction (complete or partial)
- Implant repositioning requiring surgical intervention
- Increase in cup/disc ratio of ≥ 0.3 units on slit lamp examination
- Increase in corneal thickness of $\geq 10\%$ in the presence of corneal edema
- IOP increase ≥ 10 mm Hg from baseline
- Iridodialysis
- Iritis (requiring treatment after the postoperative medication taper)
- Loss of eye
- Macular edema
- Macular puckering
- Posterior capsule opacification
- Ptosis
- Retinal complications
- Secondary surgical intervention
- Explant
- Secondary glaucoma procedure with explant
- Secondary glaucoma procedure
- Significant (2-grade) worsening or a grade of moderate or severe, for any slit lamp observation for which a standard grading scale is not available (>30 days postoperatively)
- Anterior chamber cells
- Blepharitis
- Chalazion
- Dysesthetic bleb
- Hyperemia
- Significant iris injury or atrophy
- Strabismus
- Suture abscess or other local infection
- Vitreous hemorrhage
- Vitreous loss
- Wound leak/dehiscence

5.6.3. Additional Safety Assessments**5.6.3.1. Clinical Hypotony**

CONFIDENTIAL

Draft Statistical Analysis Plan v2.0

XEN-45 Gel Stent

Clinical hypotony is defined as vision reduction (2 lines or more) related to macular changes consistent with hypotony maculopathy (macular folds), optic disc edema, and/or serious choroidal detachments because of low IOP.

5.6.3.2. Biomicroscopy and ophthalmoscopy

Findings from slit-lamp biomicroscopy and ophthalmoscopy will be recorded.

The number and percentage of participants with biomicroscopy and ophthalmoscopy findings with more than 1 severity grade increase from baseline for items with severity grade and status change from absence at baseline to presence at post-baseline visits for items without severity grade will be tabulated by preferred term in descending order of incidence rate. The number and percentage of participants with any clinically significant findings will be presented (as “Overall”) by treatment group for study eye.

The data will be presented in the subject listing if the findings are not coded in MedDRA. In addition, some information, like severity grade may not be collected, then the data will not be presented.

5.6.3.3. Best Corrected Vision Acuity (BCVA)

BCVA will be performed using a Snellen chart with glasses, and the BCVA data collected in the visual acuity eCRF page will be analyzed. The line change from baseline at each follow-up evaluation will be calculated using the following formula:

$$\text{Line change} = 10 \times [\log_{10}(20/d_{\text{follow-up}}) - \log_{10}(20/d_{\text{baseline}})]$$

Where d_{baseline} = denominator of the Snellen equivalent unit at baseline

$d_{\text{follow-up}}$ = denominator of the Snellen equivalent unit at follow-up

The logarithmic values are to be rounded to the nearest tenth before calculation of the line change. A positive value indicates an improvement and a negative value indicates a worsening.

The data for the worst line change from baseline across follow-up will be summarized by treatment group for the study eye. The worst line change is defined as the greatest decrease from baseline in the number of lines read. Summary statistics of the worst line change will be presented in each of the following categories: worsening (< -2), no change (≥ -2 and ≤ 2) and improving (> 2). The number and percentage of participants with study eye meeting criteria of each category will be presented.

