**Safety:**

- Clinical hypotony defined as vision reduction (2 lines or more) related to macular changes consistent with hypotony maculopathy (macular folds), optic disc edema, and/or serous choroidal detachments because of low IOP
- Eyes with IOP 6 mm Hg or less at any time point and relevant clinical assessment (vision reduction [2 lines or more] related to macular changes consistent with hypotony maculopathy [macular folds], optic disc edema, anterior chamber status, and/or serous choroidal detachments because of low IOP) of these eyes at those time points
- Adverse events (AEs) including specific intraoperative and postoperative events of interest
- BCVA, pachymetry, visual field
- AE including serious AEs (SAEs)
- Adverse device effects (ADEs) including serious ADEs (SADEs)

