### 8.2.2 Quality Management and Risk Evaluation

As noted in XEN's Directions for Use the complications that may occur in conjunction with the use of XEN include, but are not limited to, the following: choroidal effusion, hyphema, hypotony, implant migration, implant exposure, wound leak, need for secondary surgical intervention and other known complications of intraocular surgery (eg, flat or shallow chamber, corneal edema, endophthalmitis).

The risk profile for XEN has been established based on the review of all applicable safety data. These complications include adverse reaction to implant material, infection, implant failure, device malfunction, hypotony, flat anterior chamber (central lens, corneal touch), endophthalmitis, and ocular injury (inadvertent perforation of the sclera, hyphema, inadvertent loss of vitreous, choroidal hemorrhage or effusion, bleeding, device wound dehiscence). Risks involved in the procedure include persistent inflammation, corneal complications, retinal complications, choroidal complications, visual acuity loss (loss of 2 Snellen lines or more), chronic pain, unplanned secondary surgical intervention, loss of eye, and infection.

XEN is currently contraindicated under the following circumstances or conditions: angle-closure glaucoma, previous glaucoma shunt/valve in the target quadrant, presence of conjunctival scarring, prior conjunctival surgery or other conjunctival pathologies (eg, pterygium) in the target quadrant, active inflammation (eg, blepharitis, conjunctivitis, keratitis, uveitis), active iris neovascularization or neovascularization of the iris within 6 months of the surgical date, anterior chamber intraocular lens (ACIOL), presence of intraocular silicone oil, vitreous present in the anterior chamber. The exclusion criteria of this trial are in accordance with the contraindications for the device (see [Section 8.3.3](#)).

The risks associated with the use of XEN are considered reasonable in comparison with the anticipated benefits to subjects. XEN poses an acceptable level of risk for its intended use.

The risks associated with the gold-standard subconjunctival filtering procedure trabeculectomy have been well studied and include choroidal effusion, shallow/flat anterior chamber, wound leak, hyphema, dysesthesia, encapsulated bleb, and persistent corneal edema ([Gedde et al. 2007](#)).

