5.3.1. Definition of Primary Endpoint

The primary effectiveness endpoint is the proportion of responders meeting all criteria below:

- Achieving $\geq 20\%$ mean IOP reduction from baseline at Month 12
- No increase in number of topical IOP-lowering medications at Month 12 compared to the baseline
- No clinical hypotony
- No loss of vision to count fingers or worse
- No secondary glaucoma surgical intervention.

The IOP will be assessed at all study visits by standard Goldmann Applanation Tonometry. For each IOP assessment, two consecutive measurements will be taken for each eye. If these 2 measurements differ by > 1 mm Hg, a third measurement will be performed for the given eye. The IOP value for a given eye will be the average of all measurements, which will be obtained from the eCRF, and the percent change from baseline at Month 12 will be computed as

$$\text{Percent change} = \frac{\text{Month 12 IOP} - \text{Baseline IOP}}{\text{Baseline IOP}} \times 100$$

The subject having the computed value of ≤ -20 will be considered achieving $\geq 20\%$ mean IOP reduction from baseline at Month 12.

The usage of topical IOP-lowering medication will be collected in the concomitant medication page. The IOP-lowering medication that were started before the Month 12 visit and stopped on or after the Month 12 visit or recorded as ongoing will be considered as the medication taken at Month 12. The partial start and stop dates of the medication will be imputed based on missing dates imputation rules specified in Appendix 3.

The clinical hypotony is defined as vision reduction (2 lines or more) related to macular changes consistent with hypotony maculopathy (macular folds), optic disc edema, and/or serous choroidal detachments because of low IOP. The following steps provide the identification of a patient with clinical hypotony. A patient at any time point with the following conditions:

- 1- filter any eyes with IOP of 6 mmHg or less, from this list...
- 2- Filter any eyes with VA reduction 2 lines or more compare to baseline, from the eyes left (and this is where it becomes more clinical and difficult, but the n should not be too high at this point)...
- 3- Filter any eyes that reported on the "OPHTHALMOSCOPY CRF" abnormal macula or periphery; AND any eyes that reported any of these AE:
 - Anterior chamber shallow with peripheral irido-corneal touch
 - Anterior chamber flat with irido-corneal touch

CONFIDENTIAL

Draft Statistical Analysis Plan v2.0

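### The SAP's BCVA safety table counts an exact 2-line loss as no change, so it understates losses of 2 lines or more, the threshold both documents use elsewhere

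*SAP*

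**What the plan says.** SAP 5.6.3.3 computes line change as 10 × [log10(20/d at follow-up) − log10(20/d at baseline)], where d is the Snellen denominator. It adds: "The logarithmic values are to be rounded to the nearest tenth before calculation of the line change". On sign: "A positive value indicates an improvement and a negative value indicates a worsening". The tabulated quantity is the worst value over follow-up in the study eye: "The worst line change is defined as the greatest decrease from baseline in the number of lines read". The categories are "worsening (< -2), no change (≥ -2 and ≤ 2) and improving (> 2".

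Elsewhere the threshold for loss is 2 lines, with 2 included:

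- Protocol 8.2.2, risks of the procedure: "visual acuity loss (loss of 2 Snellen lines or more".
- Protocol Synopsis and 7.2, safety endpoints: "Clinical hypotony defined as vision reduction (2 lines or more) related to macular changes consistent with hypotony maculopathy". SAP 5.6.3.1 repeats this definition.
- SAP 5.6.2.1, adverse events of special interest, matching Protocol 10.1.2.1.2: "BCVA loss of ≥ 2 lines (≥ 10 Early Treatment Diabetic Retinopathy Study [ETDRS] letters".
- SAP 5.3.1, second step of the hypotony filter: "Filter any eyes with VA reduction 2 lines or more compare to baseline".

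**The concern.** BCVA is a named safety endpoint, and the study objective includes comparing the safety of the two operations. The worst-change table is the only summary that SAP 5.6.3.3 specifies for measured acuity. If its worsening category starts one line later than the threshold used everywhere else, an eye can meet the adverse-event definition of BCVA loss and pass the acuity step of the hypotony filter, yet be counted as unchanged here. The table would then understate loss in either arm, could blur a difference between arms, and could disagree with the adverse-event table without explanation. The SAP gives no reason for a stricter cut in this one place.

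**Working it through.** **Inputs.** The formula, rounding rule and cut-points come from SAP 5.6.3.3. Baseline acuity of 20/100 or better comes from Protocol 8.3.2, inclusion criterion 4. The documents do not list the chart lines, so I assume denominators of 15, 20, 25, 30, 40, 50, 60, 70, 80, 100, 125, 150, 200 and 400.

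**Step 1: the scale.** Each log is a multiple of 0.1, so 10 times a difference of two logs is a whole number. A score below -2 therefore means -3 or lower, and exactly -2 is an ordinary value rather than a rare tie.

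**Step 2: examples.**

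- 20/20 to 20/30: log10(20/30) = -0.176, rounded to -0.2. 10 × (-0.2 − 0.0) = -2, no change.
- 20/25 to 20/40: 10 × (-0.3 − (-0.1)) = -2, no change.
- 20/20 to 20/40: 10 × (-0.3 − 0.0) = -3, worsening.

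**Step 3: all worsening steps.** The ten baseline denominators from 15 to 100 give 13 + 12 + 11 + 10 + 9 + 8 + 7 + 6 + 5 + 4 = 85 steps to a worse line. Of these, 62 score below -2 and 73 score -2 or lower. The difference, 73 − 62 = 11, is the set filed as no change despite scoring a 2-line loss:

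| Step | Unrounded lines |
|---|---|
| 20/15 to 20/25 | -2.22 |
| 20/20 to 20/30 | -1.76 |
| 20/25 to 20/40 | -2.04 |
| 20/30 to 20/50 | -2.22 |
| 20/40 to 20/60 | -1.76 |
| 20/40 to 20/70 | -2.43 |
| 20/50 to 20/80 | -2.04 |
| 20/60 to 20/100 | -2.22 |
| 20/70 to 20/100 | -1.55 |
| 20/80 to 20/125 | -1.94 |
| 20/100 to 20/150 | -1.76 |

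Six of the 11 exceed 2 lines before rounding, and five fall short of it.

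**Step 4: stability in software.** In ordinary floating-point arithmetic (run in Python), two of the 11 steps, 20/80 to 20/125 and 20/100 to 20/150, evaluate to -2.000000000000001 and would slip into worsening under the present rule. Four others, 20/25 to 20/40, 20/50 to 20/80, 20/60 to 20/100 and 20/70 to 20/100, evaluate to about -1.9999999999999998 or -1.9999999999999996 and would be missed by a rule of -2 or lower. Identical scores could thus be classified differently unless the result is rounded first. Other software may differ in which steps are affected.

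**Step 5: weight of one eye.** The SAP plans 68 XEN and 34 trabeculectomy completers, from 76 and 38 enrolled. One reclassified eye moves an arm's worsening percentage by 1/76 to 1/68, or 1.3 to 1.5 points, in the XEN arm and by 1/38 to 1/34, or 2.6 to 2.9 points, in the trabeculectomy arm.

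**The case against.** The strongest reply is that the threshold is applied elsewhere. BCVA loss of 2 lines or more is a listed adverse event, split by timing, that investigators are told to report, and SAP 5.6.2 tabulates reported treatment-emergent events by arm. SAP 5.4.2 also gives mean change in BCVA at every visit. The table is descriptive, with no test or decision attached. A stricter cut for a worst-ever value that includes Day 1 could be a deliberate choice, and the risk list and hypotony filter do not themselves define the bins of this table.

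Much of this stands, and it limits the point. A reader might infer that losses of 2 lines or more are never shown as worsening, or are lost from the trial report. The documents do not support that: losses of 3 or more lines are shown in this table, and 2-line losses can appear as adverse events. Nor is the primary endpoint touched, because the hypotony filter states its own threshold of 2 lines or more.

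The reply still does not repair the table. The adverse-event route depends on investigator reporting in an open-label trial, and no rule derives the event from measured acuity. The hypotony filter also requires an IOP of 6 mm Hg or less and further findings, so a 2-line loss from another cause is not captured. A mean change does not count eyes. If the stricter cut was intended, the SAP does not say so.

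**Conclusion.** The point holds as a reporting inconsistency in a descriptive safety table. On the SAP's own whole-number scale, exact 2-line losses are labelled no change, against the threshold in the adverse-event list (the closest conflict), the risk section and the hypotony definition. On the assumed denominators this covers 11 of the 73 steps that score a loss of 2 lines or more. Those counts depend on the assumed chart and say nothing about how many eyes will be affected; the documents give no basis for a patient frequency. That an exact -2 falls in no change does not depend on the assumed chart, apart from the floating-point effect noted above. The table should be corrected, but nothing confirmatory rests on it.

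**What to change.** In SAP 5.6.3.3, round the computed line change to a whole number, then define worsening as -2 or lower and no change as above -2. The upper bound can stay as it is. Setting no change below 2 and improving at 2 or higher would make the bins symmetric, but that is preference: the conflicting passages concern loss only. If the stricter cut is intended, state the reason and add a row for losses of 2 lines or more.

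The change needs no new data and only a line or two of text. It has two downsides. The table may look slightly less favourable. Also, because of the log rounding, some losses under 2 unrounded lines will count as worsening, such as 20/20 to 20/30 (1.76 lines) and 20/70 to 20/100 (1.55 lines); a footnote giving the scoring rule would cover this.
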